# **Glossary of abbreviations**

| ALPHA    | Advice Leading to Public Health Advancement  |
|----------|--|
| ALSPAC   | Avon Longitudinal Study of Parents and Children  |
| ASSIST   | A Stop Smoking in Schools Trial (used here to denote the intervention, rather than the trial)    |
| CF       | Consent Form   |
| CI       | Chief Investigator   |
| CRF      | Case Report Form   |
| CRO      | Contract Research Organisation   |
| CTU      | Clinical Trials Unit   |
| CU       | Cardiff University   |
| DECIPHer | Centre for the Development and Evaluation of Complex Interventions for Public Health Improvement |
| EUCTD    | European Union Clinical Trials Directive   |
| Eu-DAP   | European Drug Abuse Prevention Trial   |
| ICH      | International Conference on Harmonization  |
| GCP      | Good Clinical Practice   |
| GAFREC   | Governance Arrangements for NHS Research Ethics Committees                                       |
| HE       | Health Economics   |
| HSE      | Health Survey for England  |
| IC       | Informed consent   |
| IDMC     | Independent Data Monitoring Committee  |
| IEC      | Independent Ethics Committee   |
| IRAS     | Intergrated Research Approval System   |
| ISRCTN   | International Standard Randomised Controlled Trial Number  |
| NIHR     | National Institute for Health Research   |
| NHS      | National Health Service  |

[figure not shown]
| NISCHR | National Institute for Social Care & Health Research |  |  |  |
|--------|--|--|--|--|
| PI     | Principal Investigator                               |  |  |  |
| PHR    | Public Health Research                               |  |  |  |
| PPI    | Patient and Public Involvement                       |  |  |  |
| PHW    | Public Health Wales                                  |  |  |  |
| PIS    | Patient Information Sheet                            |  |  |  |
| R&D    | Research and Development                             |  |  |  |
| RCT    | Randomised Controlled Trial                          |  |  |  |
| REC    | Research Ethics Committee                            |  |  |  |
| SEWTU  | South East Wales Trials Unit                         |  |  |  |
| SMT    | School Management Team                               |  |  |  |
| SOP    | Standard Operating Procedure                         |  |  |  |
| TMF    | Trial Master File                                    |  |  |  |
| TMG    | Trial Management Group                               |  |  |  |
| TND    | Towards No Drug abuse                                |  |  |  |
| TSC    | Trial Steering Committee                             |  |  |  |
| UKCRC  | United Kingdom Clinical Research Collaboration       |  |  |  |

# 1 Amendment History

| Amendment
No. | Protocol version no. | Date
issued | Author(s) of changes | Details of changes made |
|------------------|----------------------|----------------|----------------------|-------------------------|
|                  |                      |                |                      |                         |

[figure not shown]
# 2 Synopsis

| Full title           | Adapting and piloting the ASSIST model of informal peer-led intervention delivery to the Talk to Frank drug prevention programme in UK secondary schools (ASSIST+Frank): an exploratory trial   |  |
|----------------------|---|--|
| Acronym              | ASSIST+Frank  |  |
| Study design         | This project will have 3-stages:  |  |
|                      | Stage 1: Development of training materials and an intervention manual for ASSIST+Frank and Frank friends;   |  |
|                      | Stage 2: Piloting of ASSIST+Frank in one school and Frank friends in one school followed by a period of refinement of the interventions;  |  |
|                      | Stage 3: Exploratory 4-arm trial with cluster randomisation (at the level of school) in 12 state secondary schools in South Wales with an embedded process evaluation.  |  |
| Study participants   | Students aged 12-13 (year 8) at baseline in state secondary schools.  |  |
| Planned sample size  | The total sample size of 12 schools for the exploratory trial is anticipated to equate to approximately 2040 students (assuming a 170 pupils in a year), which with a response rate of 80% will achieve a sample of 1632 students (408; 408; 408; 408 per arm). If the average year group had 150 students, we would expect 1800 to be sampled, and with an 80% response rate 1440 to participate, equating to 360 per arm. |  |
| Follow-up duration   | 18 months   |  |
| Planned study period | 1 st March 2014 to 31 st October 2016   |  |
| Primary aim          | To assess the feasibility and acceptability of delivering the ASSIST+Frank adjunct and Frank friends interventions to determine whether to proceed to a full-scale RCT.   |  |
| Interventions        | ASSIST is an informal peer-led smoking prevention intervention to diffuse and sustain non-smoking norms via secondary school students' social networks in year 8.  ASSIST Frenk is an informal peer led drug prevention adjunct to  |  |
|                      | ASSIST+Frank is an informal peer-led drug prevention adjunct to ASSIST designed to be delivered in year 9 in secondary schools to the year groups who have previously received ASSIST in year 8.  |  |
|                      | Frank friends is a stand-alone, informal drug prevention intervention   |  |

[figure not shown]
# 3 Trial/ summary & study schema

## 3.1 Study schema a

<sup>a Note: Stages will not take place in chronological order. ASSIST will be delivered in year 8 and the baseline data collection for the exploratory trial (stage 3) will take place before the piloting of ASSIST+Frank and Frank friends.

# 3.2 Participant flow diagram

#### 3.3 Study summary

## **Background**

School-based drug prevention interventions have historically focused on abstinence, been delivered by school teachers or law enforcement officers, and had limited effectiveness in terms of behaviour change. Informal school-based peer-support has been effective in preventing the uptake of smoking but evidence on the prevention of illicit drug use using peer support is inconclusive.

#### Aims

The primary aim of this project is to develop, pilot and assess the feasibility, acceptability and delivery of two new, informal peer-led interventions designed to prevent illicit drug use among secondary-school students, as well as to assess trial recruitment and retention rates. We will evaluate the effect of these peer-led drug and a peer-led smoking intervention on the: incidence of drug use (primary outcome); the frequency of use of any and specific drugs; cannabis dependence; incidence of smoking; smoking frequency; nicotine dependence; and alcohol use. These data will not provide any indication of effectiveness but will give an indication of trial feasibility, effect-sizes, and potential mechanisms of action to inform the design of a definitive phase three trial.

# Design

Intervention development, piloting and cluster randomised controlled exploratory trial (MRC complex intervention phase II trial). Two drug prevention interventions (ASSIST+Frank and Frank friends) will be developed using the peer nomination and training manual from an existing effective peer-led smoking prevention intervention, ASSIST; content on drug misuse will come from the UK national drug education service, "Frank". (www.talktofrank.com). ASSIST+Frank and Frank friends will be piloted in one school each and be followed by a process evaluation and period of intervention refinement. A 4-arm cluster exploratory RCT (ASSIST in year 8 with ASSIST+Frank adjunct intervention in year 9; ASSIST in year 8 only; Frank friends in year 9 only; usual care comparison) will then be conducted, with an embedded process evaluation

#### **Population**

Students aged 12-14 in state secondary schools.

#### Outcome measures

Within the exploratory trial, a mixed methods process evaluation will be used to assess each intervention against pre-defined progression criteria (to be agreed by the Trial Steering Committee) based on: 1) the feasibility of delivering ASSIST+Frank and Frank friends; 2) the acceptability of ASSIST+Frank and Frank friends to peer supporters; 3) the acceptability of the interventions to school senior management teams, other school staff, and parents; and 4) acceptability of trial design and assessment methods. Numbers of schools and participants recruited and retained will be presented as well as data on intervention fidelity. The indicative primary effectiveness outcome will be the incidence of any drug use assessed 18 months post randomisation. Secondary outcomes include the frequency of use of any and specific drugs; cannabis dependence; smoking frequency; nicotine dependence; and changes in social networks of peer drug and tobacco use.

#### Duration and follow-up

Following the development, piloting and refinement of ASSIST+Frank and Frank friends participants in the exploratory trial will provide consent and complete a baseline self-report questionnaire. Students randomised into the ASSIST and ASSIST+Frank arms will receive ASSIST in year 8. Approximately 6 to 12 months after the delivery of ASSIST, during year 9, students will receive the ASSIST+Frank and Frank friends arms interventions. 18 months post randomisation participants will complete the follow up questionnaire to assess any change in drug use.

#### 4 Introduction

#### 4.1 Background

The NIHR commissioning brief PHR no 12/3060 noted that peer-support has been effective for alcohol and smoking but evidence on the prevention of illicit drug use using peer support is inconclusive. This led to a call to answer the research question: "What is the effectiveness and cost effectiveness of using peer support to prevent illicit drug uptake and use in young people?" We identified two systematic reviews (1)(2) and two RCTs not included in these

reviews (3)(4) which had used peers support to prevent drug misuse in young people and these informed the aims, objectives, design and methods of the study. These reviews and studies are summarised below.

Systematic reviews evaluating peer-led drug prevention interventions with adolescents: A Cochrane review of schools-based drug prevention interventions examined the effects of peer-led versus teacher-led interventions (1). Based on one RCT of the Life Skills programme, this review suggests that drug prevention in schools may be more effective when delivered by peers (5). This version of the Life Skills programme focused on fostering self-esteem, confidence and independent decision-making in addition to drugs education. Peer-leaders were aged 14-16, and either volunteered to participate, or were recruited via teacher-nomination. Following training, peer-leaders were asked to deliver a 20-session programme to 11-12 year old students at their school. After four months (5) and one year (6) fewer students reported using marijuana in the past month in the peer-led than control arm.

Mentoring to prevent illegal drug use: A separate 2011 Cochrane review of mentoring programmes to prevent drug use included 4 RCTs but a pooled effect was not estimated due to heterogeneity in drug use measures (2). Only one programme had a peer-led component relevant to a school-setting, involving older peers providing social support to youth 10-16 years of age. The 'Big Brothers Big Sisters Programme' was effective in preventing the uptake of any drug use among young people reporting never having used drugs at baseline (7).

RCTs of school-based drug prevention: Two RCTs were identified which included peer-led components within a drug prevention curriculum either to deliver additional sessions (4), or review teacher delivered content at each session (3). The European Drug Addiction Prevention (EU-DAP) study was a 4-arm RCT in 170 schools (N=7079, students 12-14 years of age) that examined the effectiveness of a 12-hour curriculum to reduce substance use across seven countries. The four arms were: a) teacher-delivered curriculum (TDC) only; b) TDC with seven additional peer-led sessions; c) TDC plus three workshops for parents; and d) a control. Schools were instructed to select same age peers either by teacher nomination or

student vote. After 18-months, multilevel models showed a weak effect on lifetime cannabis use (OR = 0.83; 95% CI = 0.65, 1.05; NNT = 34) and frequent cannabis use ( $\geq 3$  occasions in past 30 days; OR = 0.74; 95% CI = 0.53, 1.00; NNT = 46) in students allocated to any active arm (i.e. a-c) versus the control arm. A null effect was reported for allocation to the peer-led and parent arm on cannabis use and results were not tabulated because programme implementation was very low in the peer-arm. Only 8% of centres implemented all seven peer-led sessions and 71% did not conduct any meetings at all. This suggests these estimates on effectiveness of the peer-led arm are unlikely to be precise. Also that interventions using formal peer-led delivery should undergo extensive piloting and testing to explore the acceptability and feasibility of delivering the intervention with peer-supporters.

A three-arm RCT of the Towards No Drug Abuse (TND) programme (8), examined the additional benefit of adding a peer-led review of intervention materials at the end of 12 sessions delivered by teachers (3). TND emphasises improving education on the risks of drug use, decision making and self-control. High-school classes (n= 840 students; mean age 16) were randomized to: a) standard TND curriculum; b) standard TND curriculum with a peerled component (TND-Network); a control. Peer-leaders were those receiving the most nominations regarding "who would make the best leaders for a project in class". Groups were then created within each class by assigning students to a leader whom they had chosen, or to whom they were socio-metrically closest (9). Compared with controls, students in the TND arm did not report a significant change in their drug use, but those in the TND Network arm reported a reduction in the frequency of cannabis and cocaine use in the past month at a one year follow-up. An interaction between allocation to TND-Network vs. control arm and peer substance use (i.e. the average use of tobacco, alcohol, cannabis and cocaine reported by the five classmates nominated as friends) revealed that the intervention was most effective for students embedded in peer networks that did not engage in substance use. Those students with friends who had already used substances in the TND-network arm were more likely to increase their use suggesting the potential for harms via the diffusion of pro-drug norms in poorly designed peer-led interventions. However, contamination is a major methodological weakness in this trial which allocated classes (rather than year group or schools); therefore the effect of TND network in this comparison may have been diluted (3).

#### 4.2 Rationale for current study

We only identified three RCTs using peer support to prevent illicit drug use with two positive (3)(6) and one non-significant result (4). Due to the low levels of intervention implementation in one trial (4), and a potentially harmful effect observed for high risk groups in another (3), these studies suggest that, while peer-led drug prevention interventions are promising, modifying the peer-led components may be warranted to optimise peer support for drug prevention with young people.

ASSIST is an effective, informal peer-led intervention for smoking prevention delivered in secondary schools (10). Based on diffusion of innovation theory (11) it purposively recruits 'influential' students aged 12-13 years (UK year 8) and trains them as 'peer supporters' to spread and sustain non-smoking norms through informal conversations with their peers. A cluster RCT in 59 schools (n=10,730) in 2001-2004 found that it reduced weekly smoking among students over a 2-year period; including smoking frequency among students who had ever smoked before (10).

We will develop an additional component of the ASSIST smoking prevention intervention to be delivered in year 9 when students are aged 13-14. The ASSIST+Frank adjunct intervention will involve one additional day of training of former ASSIST peer supporters to develop the skills to discuss drug use with their peer group. We will also develop a standalone drug prevention version of ASSIST to be delivered in year 9, Frank friends. Frank friends will replicate the ASSIST model of peer recruitment and training but replace content on the harms associated with smoking tobacco with information on drug use. In the +Frank and Frank friends interventions peer supporters will be educated on the harms associated with drug use and how to minimise the known harms amongst their friends. The drug use content will come from the Talk to Frank website (www.talktofrank.com). Talk to Frank is the UK national drug education service and provides up-to-date, youth-friendly information and advice on the risks and harms of drug use.

It is important to note that there are differences between the intervention we propose and the approaches used in the EU-Dap and TND-Network interventions. Firstly, the ASSIST model is an informal method of delivery which asks influential peers to talk about substance use behaviour (currently smoking) with friends during conversations in naturally occurring contexts, rather than via leading formal sessions in classrooms. Secondly, as well as standard education on the risks of drug use, Talk to Frank provides advice on minimising the harms

associated with drug use through multiple, interactive methods (e.g. text messaging, telephone, email, and anonymous web-chat) that may be better suited as an adjunct to peer communication than classroom-based advice.

An unpublished feasibility trial of a drug prevention intervention based on the ASSIST model (CASE+) found little change in intentions to use cannabis in 732 12-13 year old students (in six Scottish secondary schools) over a three month follow-up (12). However, there are a number of factors which limit the relevance of this trial to this study, a) no drug use data were collected, b) three month follow-up is not long enough to ascertain the likely effect over longer periods, and, c) intervention content was solely on cannabis use. The intervention added one extra day of education solely on cannabis use to the existing two days of training on smoking in ASSIST. A process evaluation indicated that although implementation fidelity and acceptability with school staff was high, the addition of the extra day of training on cannabis at the same time as the training on smoking had two unhelpful effects. First, the three-day training attempted to deliver too much information. This distracted students from engagement with key messages and reduced the time spent on developing the peer supporters' skills in having conversations with their friends. Second, the peer supporters rarely had conversations about cannabis, since given the choice of discussing smoking or cannabis use, it was easier for them to opt to focus on smoking, because there were few students experimenting with cannabis at age 12/13, and there was a sensitivity around discussing cannabis use as it is illegal. This study indicated that tackling both behaviours at the same time was problematic, and that peer supporters needed additional training and support to engage in conversations about cannabis as confidently as they were able to do around tobacco use.

The proposed ASSIST+Frank extension is quite different to CASE+, in that the ASSIST smoking prevention intervention will be implemented in year 8, with the additional drug focus and Talk to Frank materials (ASSIST+Frank) being introduced to those same peer supporters in year 9, one year later. A process evaluation following the piloting and an exploratory trial will explore whether the ASSIST+Frank and Frank friends intervention are acceptable and peer supporters are adequately informed and supported to disseminate the harm minimisation message from Talk to Frank. Exploratory analysis will also examine the relative effectiveness of these interventions in preventing and reducing drug use against a usual care control. An arm of ASSIST only schools will also be included in the exploratory

trial to examine the potential unintended beneficial effects of a smoking prevention intervention on drug use, in particular cannabis use which is typically used with tobacco.

# 5 Study aim and objectives

# 5.1 Primary aim

To assess the feasibility and acceptability of delivering the ASSIST+Frank adjunct and Frank friends interventions to determine whether to proceed to a full-scale RCT.

# 5.2 Study objectives:

- assess and refine the ASSIST logic model so that it is applicable to drug prevention;
- assess the acceptability of the intervention and evaluation to ASSIST+Frank and
   Frank friends trainers, students, parents, and school staff;
- explore the barriers and facilitators of implementing the interventions;
- explore the fidelity of intervention delivery by ASSIST+Frank and Frank friends trainers and peer supporters;
- explore whether the proposed outcome measures are suitable for assessing illicit drug
   use (primary outcome) and the secondary outcomes of interest;
- assess trial recruitment and retention rates;
- identify potential effect sizes that are likely to be detected as part of a definitive trial and an appropriate sample size;
- record the delivery costs and to pilot methods for assessing cost effectiveness;
- identify the structures, resources and partnerships necessary for a definitive trial to take place;
- to develop the protocol for a definitive trial and economic evaluation of the impact of ASSIST+Frank and Frank friends compared to usual advice provided in schools to reduce illicit drug use.

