# 6 Study design

This proposed project has 3-stages (see above study schema on page 14):

Stage 1: Development of training materials and an intervention manual for ASSIST+Frank and Frank friends;

Stage 2: Piloting of ASSIST+Frank in one school and Frank friends in one school followed by a period of refinement of the interventions;

Stage 3: Exploratory 4-arm trial with cluster randomisation (at the level of school) in 12 state secondary schools in South Wales with an embedded process evaluation.

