#### 9.6 Randomisation

In the exploratory trial, randomisation of schools will occur after all schools have completed baseline data collection. Schools will be randomly assigned to one of the 4 arms with an assignment ratio of 3: 3: 3: 3. Allocation will be conducted by an independent SEWTU statistician, blind to the identity of schools, and minimised on: the percentage of pupils in receipt of free school meals and school size to balance the randomisation. Optimal allocation will be used to carry out the randomisation. Here a balance algorithm is used when predefined sequence generation is required or when all units are randomised jointly. Data on school size and free school meal entitlement will be collected at recruitment and used to balance the randomisation.

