#### 14 Statistical considerations

#### 14.1 Sample size

The total sample size of 12 schools for the exploratory trial is anticipated to equate to approximately 2040 students (assuming a 170 pupils in a year), which with a response rate of 90% (based on 1-year follow-up in the RCT of ASSIST (10), will achieve a sample of 1632 students (408; 408; 408 per arm). If the average year group had 150 students, we would expect 1800 to be sampled; 1440 respond with an 80% response rate, equating to 360 per arm. The choice of 12 schools will provide some information on variability within and between schools at baseline and follow-up. This sample is not anticipated to provide adequate

power to detect a statistically significant difference across groups, as this is an exploratory trial. However, the sample will indicate the likely response rates, and permit estimates (with 95% confidence intervals) of likely effect sizes, and intra-cluster correlations (ICCs) of drug incidence in each group in anticipation of a larger trial.

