## 15 Analysis

### 15.1 Main analysis

The statistical analyses will be primarily descriptive, providing a realistic estimate of eligibility, recruitment, intervention delivery and retention rates in the study population. We will analyse key secondary outcomes that are more immediate targets of the intervention (e.g. knowledge of the harms of drug use; mean peer level drug use) to consider the potential of the intervention. We will undertake mediator analysis to see if the identified pathways in the logic model are associated with the uptake of drug use. Individuals lost to follow-up will be compared to those who complete follow up to identify any potential biases.

An intention to treat (ITT) analysis will compare the prevalence of any drug use across the 4-arms using a two-level logistic regression model to account for clustering within schools. The main analysis will examine prevalence of any drug use at 18 months. The baseline prevalence of any drug use, as well as age, sex, free school meal entitlement, and family affluence will be included as covariates. As an exploratory trial the proposed analysis is not powered to provide a definitive comparison between the intervention and control groups and as such p-values will not be presented. An exploratory analysis will nevertheless be undertaken. We will model comparisons between: a) ASSIST and the usual care control (to examine any unintended effects of ASSIST on drug use), b) ASSIST+Frank and the usual care control, c) Frank friends and the usual care control, and d) ASSIST and ASSIST+Frank to estimate the added value of the Talk to Frank content. These key trial parameters will inform the power calculations for a future definitive trial.

Between-group comparisons for secondary outcomes will be modelled similarly using either linear (e.g. frequency of drug use) or logistic (e.g. cannabis dependence) regression models with the focus on 95% confidence intervals to estimate possible effect sizes.

Exploratory analysis will consider the impact of demographic factors as well as other theoretical moderators on the intervention effect using interaction terms included in the main

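### Between-arm drug-use estimates from three schools per arm are to inform the definitive trial's effect size and power calculation, and no outside target difference is named

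*Protocol*

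**What the plan says.** Section 6 describes an "Exploratory 4-arm trial with cluster randomisation (at the level of school) in 12 state secondary schools in South Wales", and section 9.6 allocates them 3:3:3:3, so each arm has three schools.

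Three places give the between-arm estimates a planning role:

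- Section 5.2 lists as an objective to "identify potential effect sizes that are likely to be detected as part of a definitive trial and an appropriate sample size".
- Section 14.1 expects the 12 schools to yield interval estimates of the arm differences, together with "intra-cluster correlations (ICCs) of drug incidence in each group in anticipation of a larger trial".
- Section 15.1 lists ASSIST, ASSIST+Frank and Frank friends each against usual care, and ASSIST against ASSIST+Frank. It then continues: "These key trial parameters will inform the power calculations for a future definitive trial".

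The protocol is open about the limits. The Aims paragraph in section 3.3 says "These data will not provide any indication of effectiveness but will give an indication of trial feasibility, effect-sizes". Section 14.1 concedes inadequate power, and section 15.1 withholds p-values. Section 15.4 adds that cost-effectiveness data may also feed the later sample size. Nowhere is a minimum worthwhile difference, or an effect from another source, named as the basis for the definitive trial.

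**The concern.** A between-arm effect size is an estimate of effectiveness. If the data cannot indicate effectiveness, they cannot indicate the effect size to plan for either. Conceding low power and omitting p-values guards against over-claiming in this trial, but does not stop the estimate from sizing the next one.

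With three schools per arm, the estimate depends heavily on which schools fell into which arm. Required sample size varies roughly with the inverse square of the planned difference, so a modest chance exaggeration gives a much smaller trial. What is at stake is a definitive trial of the wrong size, most often too small.

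**Working it through.** **The plan's own figure.** 12 × 170 = 2040 pupils; 2040 × 0.80 = 1632; 1632 / 4 = 408 per arm; 408 / 3 = 136 per school. This reproduces the Synopsis. (Section 14.1 reaches the same 1632 from a stated 90%, which would give 1836. That is a separate slip and does not matter here.) With 150 pupils per year: 1440, or 360 per arm and 120 per school. No precision or power figure is stated.

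**Inputs**

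- Schools per arm: 3 (section 9.6).
- Pupils per school: 136 from above. A low value of 102 results if the 75% follow-up response floor in section 8.1 is applied to the 136 (136 × 0.75 = 102); that reading is mine.
- True odds ratio: 0.83, reported in section 4.1 for lifetime cannabis use in a 170-school trial.
- Assumed, because the protocol gives neither: control-arm use at 18 months 10% (range 5-15%) and ICC 0.02 (range 0.01-0.05).

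**Precision by formula, central case, 136 per school**

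- Control odds 0.10/0.90 = 0.1111; × 0.83 = 0.0922; intervention proportion p1 = 0.0844.
- Design effect = 1 + (136 − 1) × 0.02 = 3.70; effective size 408 / 3.70 ≈ 110 per arm.
- SE(log OR) = √{3.70 × [1/(408 × 0.0844 × 0.9156) + 1/(408 × 0.10 × 0.90)]} = √{3.70 × (0.0317 + 0.0272)} = 0.467.
- Expected 95% interval: 0.83 × exp(±1.96 × 0.467) = 0.33 to 2.07.
- Chance of the wrong direction: Φ(ln 0.83 / 0.467) = Φ(−0.40) ≈ 34%.

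**Simulation.** Beta-binomial, three schools against three, 40,000 pilots per setting:

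| Control use | ICC | Per school | Central 95% of pilot ORs | OR above 1 | Favourable difference more than twice the truth |
|---|---|---|---|---|---|
| 10% | 0.02 | 102 | 0.30-2.22 | 34% | 35% |
| 10% | 0.02 | 136 | 0.32-2.10 | 33% | 35% |

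Over the whole grid (5-15% use, ICC 0.01-0.05, both school sizes) the wrong-direction share is about 27% to 40% and the favourable exaggeration share about 27% to 42%. Small differences between runs are simulation error.

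**Larger true effect.** At OR 0.6 with 136 per school, the wrong-direction share over the same grid is about 6% to 28%.

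**Effect on planning.** Central case, two-sided 5%, 80% power, two-proportion formula, then × 3.70 / 136 for schools:

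- OR 0.83: 5424 per arm before clustering; 5424 × 3.70 / 136 ≈ 148 schools per arm.
- A pilot estimate one SE too favourable, 0.83 × exp(−0.467) = 0.52: 544 per arm; 544 × 3.70 / 136 ≈ 15 schools per arm.
- Doubling the true difference (0.0156 to 0.0312) divides the required number by about 4.

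**ICC.** Approximate SE = √{2(1 − ρ)²[1 + (m − 1)ρ]² / [m(m − 1) × df]}. With ρ = 0.02 and m = 136 the numerator is 2 × (0.98 × 3.70)² = 26.3.

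- One arm, 2 df: √(26.3 / 36,720) = 0.027.
- Pooled within arms, 12 − 4 = 8 df: √(26.3 / 146,880) = 0.013.

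**The case against.** **Informing is not setting.** A reader might infer that the pilot estimate will fix the definitive sample size. Section 15.1 says only that the parameters will inform it, sections 14.1 and 15.1 stress confidence intervals, and section 15.4 allows another input. The objective's phrase about effects likely to be detected can even be read as detectable effects. This stands, and the point is worded accordingly. What remains is that the effects do feed the calculation and no other source for the target difference is given. An interval of about 0.3 to 2.1 cannot supply a planning value.

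**No intervention is dropped on this estimate.** A reader might also infer that a promising intervention could be wrongly abandoned, or that only pilots with favourable effects proceed. The documents do not support that. The seven criteria in section 8.1 concern delivery, acceptability, randomisation, school retention and response; none uses a drug-use effect.

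**Counting both tails exaggerates.** About 47% of pilots show a difference more than twice the true size in either direction, but about 12 percentage points of that point to harm, and nobody would size a smaller superiority trial from those. Only the favourable share, about 34%, is relevant.

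**The true effect and the adjustment.** The 0.83 compares any active arm of a mainly teacher-delivered programme with control, on lifetime cannabis use, so it is only a guide to effects here. A larger effect would show its direction more reliably, as the OR 0.6 figures show. Covariate adjustment and balanced allocation should reduce between-school variance. Yet even with an ICC of zero the formula gives a wrong direction in 15% to 30% of pilots at OR 0.83 (control use 5-20%).

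**The ICC wording is ambiguous.** In section 14.1 the reference to each group may attach to drug incidence, and the two-level model in section 15.1 would ordinarily give one common between-school variance. Separate ICCs from three schools each are a possible reading, not an established plan.

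**Conclusion.** The concern holds in a limited form. The protocol gives between-arm estimates from three schools per arm a role in the definitive trial's effect size and power calculation, and names no outside target difference. For a true effect of the size cited in section 4.1, such an estimate is on the wrong side of 1 in about a third of pilots. In about another third it more than doubles the benefit. These shares rest on assumed prevalence and ICC and on unadjusted simulation. They shrink for larger effects, so it would be too strong to say that the pilot can never show direction.

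The consequence falls on the next trial's size, mainly as undersizing. This trial's conduct, primary aim and progression decision are not affected. It should be corrected, because the text invites the misuse and the correction is cheap.

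**What to change.** - **Section 5.2 objective and the last sentence of the comparison paragraph in 15.1:** state that the definitive trial's target difference will be a justified smallest worthwhile difference, set from outside evidence and stakeholder judgement.
- **What the pilot supplies:** control-arm drug use, response, retention, and one between-school ICC pooled within arms over the 12 schools, with its confidence interval.
- **Section 14.1:** make clear whether the reference to each group applies to incidence or to the ICC, and specify the single pooled ICC.
- **Between-arm estimates:** continue to report them with 95% confidence intervals, and state that their point estimates will not be used as the target difference.

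The cost is wording only, with no change to design, recruitment or data collection. The downside is that the target difference must be justified from another source.
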